Validation protocol of foot orthoses for abnormal plantar arch using a new non-invasive clinical imaging system

Presented to the Véritas IRB Research Ethics Committee

TOPMED

Version 02

Approved in french on September 23rd 2022

Translated on June 26th 2025

NCT05163418

SCHEDULED START AND END DATES

September 2021 to June 2023

RESEARCH PROJECT DESCRIPTION

Issues

Plantar arch deviations, flat feet or hollow feet, are common problems that lead to loss of stability, poor posture and gait, and are thus at the root of many ailments and injuries. Cryos Technologies Inc. is a Quebec-based company specializing in the development of custom-made 3D foot orthotics, as well as equipment to promote the efficient production and fitting of these orthotics.

State of knowledge and project relevance

Made up of 26 bones and supporting up to 70kg/cm², the foot is the foundation of the body. It holds the whole in balance thanks to just three points of support. Any misalignment, however minor, has repercussions for the whole body. The abnormal tension caused by this imbalance is amplified from one joint to the next. Ankles, knees and hips, as well as muscular chains, can be disrupted, resulting in a change in the person's overall posture and potentially causing pain.

Foot orthotics, regardless of how they are produced (molded or 3D printed), are the standard in the treatment of foot pain and pathologies, including hollow feet and flat feet. A foot orthosis is a custom-made orthopedic insole that fits into a shoe and is applied to all or part of the plantar surface. By restoring balance between the foot's three support points, the foot orthosis helps stabilize joints and rebalance muscular tension.

Cryos' unique process, from digital impression taking to software design to orthotic printing, offers the many advantages of digital methods over conventional manual methods: speed of execution, elimination of consumables (space saving, no waste production, no water use), reproducibility, precision and reliability of volumetrics. The Cryos global system, which combines the Cryovizion posture analysis system with the production of Cryos foot orthotics, is already in use in several podiatry establishments, but has never been formally validated in terms of the effect of manufactured orthotics and postural analysis.

Research objectives

The aim of this project will be to validate a new non-invasive clinical imaging system for assessing the effectiveness of foot orthoses and to evaluate the biomechanical effectiveness of foot orthoses for flat-footed and hollow-footed people. The cryovizion system should detect changes in participants' posture with 95% accuracy, while the orthoses should improve the body's postural symmetry index.

Financing

The project was funded by NSERC's Strengthening College and Community Innovation program in partnership with Cryos Technologies Inc.

Partner company

Cryos Technologies Inc.

[name], Technical Manager

[name]

[contact]

[contact]

RESEARCH METHODOLOGY

Research location

On TOPMED's premises at Collège Mérici, [name].

Type of test

Repeated measurements on a single group with pre-tests and follow-up at 2, 6 and 12 months.

Measurement, assessment and data collection tools

Assessment :

An orthotist will take measurements and photos of the participants' feet, and assess their range of motion.

Scanning :

A Cryoscan 3D optical scanner (<https://www.cryos.com/en/professionals/cryoscan-3d/>) will be used to generate digital impressions of the participants' feet. These prints will be used to extract statistical data on morphological proportions and to model custom orthotics. This measurement system is non-invasive and harmless to health.

Analysis of walking pattern :

The *Vicon* motion capture system will provide more precise data as participants walk. The system consists of 8 infrared cameras that triangulate the exact spatial position of the sensors, which will be strategically positioned at anatomical landmarks on the participants' lower limbs. (<https://www.vicon.com/about-us/what-is-motion-capture/>). This validation system is non-invasive and harmless to health.

Load distribution between the legs will be analyzed using two AMTI force platforms (<https://amti.biz/AMTIpibrowser.aspx>).

Assessment of body symmetry will be performed using Cryovizion©, a non-invasive medical imaging tool (<https://www.cryos.com/produits/cryovizion/>). The Cryovizion imaging system uses LED light technology combined with a soft-tissue reflection enhancement filter following primary imaging, which generates a secondary image where color tones on skin surfaces vary according to distance from the camera. During image capture, subjects are instructed to stand up straight, wearing their underwear. Images are acquired from the front, side and back, from head to toe.

Questionnaires :

Subjective questionnaires and a logbook will be completed by participants to validate comfort when wearing the orthosis, and to target the extent to which and how pain is reduced.

Estimated duration of participants' activities

People with normal arches

1st session : 2h

People with flat or hollow feet

1st session : 1h to 1h30

2nd session : 2h

12-month trial phase

Telephone call (2 weeks): 5 minutes

3rd session (2months) : 1h30 to 2h

4th session (6 months) : 1h30 to 2h

5th session (12 months) : 1h30 to 2h

PARTICIPATION OF LIVE HUMAN, ANIMAL OR MATERIAL PARTICIPANTS

80 human participants aged between 18 and 50 will be recruited. Participants will be divided into three distinct groups: 20 participants with feet having a normal arch (control group), 30 participants with flat feet and 30 participants with hollow feet. The first session will be devoted to taking anthropometric measurements of the limb to be instrumented. The second session will be used to try on and adjust the orthoses, and to take pre-test biomechanical data. The following three sessions will be follow-up visits, and will consist in taking biomechanical data

Inclusion criteria

- Common
 - o Between the ages of 18 and 50
 - o BMI<30
 - o No pain
 - o No musculoskeletal problems
 - o No balance problems
 - o No central nervous system pathologies
 - o No drugs that affect balance
- Participants with flat feet
 - o Flat feet according to foot posture index 6 (FPI6, confirmed by clinical assessment)
- Participants with hollow feet
 - o Hollow feet according to foot posture index 6 (FPI6, confirmed by clinical assessment)

Exclusion criteria

- Common
 - o People with foot pathologies other than arch pathologies;
 - o Diabetics ;
 - o Severely obese people ;
 - o People who regularly wear high-heeled shoes;
 - o People with degenerative diseases ;
 - o People with neuromuscular pathologies ;
 - o People with circulatory disorders ;
 - o People who have had major lower-body surgery.
 - o Inability to walk for 30 minutes continuously.

SCIENTIFIC JUSTIFICATION FOR USING LIVE SUBJECTS

The participation of human participants representative of the clientele is essential for validation of the imaging system and evaluation of the foot orthoses. The acquisition of comparison data with a validated system will enable us to validate the biomechanical effects of the orthoses observed thanks to the Cryovizion system, and follow-up over several months will also enable us to determine the biomechanical effect of the orthoses over the medium term.

RECRUITMENT

Postings will be made in private orthotics and prosthetics laboratories, in traditional media, on social media and on the Collège Mérici bulletin boards. Candidates can express their interest by calling or writing to TOPMED. A member of the project team will be able to answer questions, assess eligibility, send documentation and/or arrange a telephone appointment at a later date.

RISKS AND DRAWBACKS, AND PROPOSED MITIGATION MEASURES

An allergic skin reaction (redness) due to wearing the brace is a potential injury. The participant should stop wearing the brace, if necessary.

Ecchymosis or phlyctena may appear at certain pressure points due to poor orthosis fit or incorrect placement. A follow-up telephone call will be made after 2 weeks' wear to ensure that the participant is comfortable with the fit. If any subsequent discomfort is experienced, the participant should stop wearing the brace and contact the orthotist.

No potential damage when capturing data with the Cryovizion system.

ADVANTAGES AND BENEFITS

The advantage of their participation is that it will provide empirical data on the system and on orthotic wear. This is an advantage for Cryos Technologies Inc.

FREE AND INFORMED CONSENT

The consent form will be provided and explained to them when they make the appointment for the 1st session. A period of two (2) weeks, or more if necessary, will be allowed to give the participant time to read and reflect. At the 1st session, a paper consent form will be handed out and explained point by point by the orthotist, before the participants decide whether or not to sign it.

CONFIDENTIALITY AND PROTECTION OF PERSONAL INFORMATION

The information collected in the questionnaires, the video captures by the Vicon system, the photos and the biomechanical data collected are confidential and will only be used in the context of this research project, unless otherwise agreed by the participant. All data, notes and computer recordings (including the Cryovizion system, photos, Vicon motion capture and foot scans) are encrypted on servers. Unless required by law, no information that could directly or indirectly reveal their identity will be released or published without their prior explicit consent.

The data will be kept for a period of five (5) years, then anonymized in a database for retention for a period of ten (10) years for the purpose of reference statistics.

Surnames, first names, telephone numbers and/or e-mail addresses will be collected for communication purposes exclusively related to this project. Participants will not be identified by name in trial documentation. They will be assigned a number, relative to the order of their recruitment, which will be used to reference the data collected. The list of codes linking a name to a research file will be kept in the office of the responsible researcher, in a locked filing cabinet at TOPMED at Mérici Collégial Privé, [name].

Any scientific publication resulting from this research project will present statistical data only, and under no circumstances will the names of the participants be published or divulged to anyone.

CONTINUOUS EXAMINATION

Should any inconvenience arise following the completion of the prototype validation test, participants will be promptly notified.

DISSEMINATING RESULTS

No disclosure to patients will be made following the trials.

Results will not be published.

COMPENSATION

No remuneration will be paid. If necessary, a parking sticker will be provided to participants during their sessions. Compensation of \$25 per participant in the control group. A compensation of \$200 per participant for the hollow/flat feet group will be given for their full participation in the validation protocol. This amount will be distributed over the last four sessions (\$30 at the 2nd session, \$40 at the 3rd session, \$50 at the 4th session and \$80 at the 5th session). In addition, participants in the hollow/flat foot group will be able to keep their foot orthotics if they complete all sessions.

RESPONSIBILITY

The legal rights of each participant will be maintained.

PROTOCOL SEQUENCE

Display

Postings in private orthotics and prosthetics labs, traditional and social media, on our website and on Mérici College bulletin boards

0241_CrA_Recrutement_Affichage_Normaux_V2

0241_CrA_Recrutement_Affichage_PlatsCreux_V4

Admission

Validation by e-mail or telephone.

0241_CrA_Recrutement_Formulaire_Admission_VF

Appointment: 2 weeks (or more if necessary) between delivery of consent form and first session.

Sending documents :

- *Hygiene_clinical measures*
- *Self-evaluation_visitor form*

Sending documents and explanations :

- *0241_CrA_Rencontre1_Consent_form_VF*

COVID call

A self-assessment confirmation will be issued 24 hours before each session.

Sessions schedule

The following abbreviations stand for the different conditions under which measurements are taken: PN = barefoot; SO = shod without orthotics; AO = shod with orthotics.

	Control	flat/hollow	documentation
Session 1	FPI6 Joint assessment Cryovizion PN+ SO Vicon PN+ SO	FPI6 Joint assessment Cryoscan3D (impression) Cryoscan2D Cryovizion PN	0241_CrA_Rencontre1_Consent_form_VF Compensation \$25 for inspection only
Session 2 (Day 0)	No session for this group	OP delivery Cryovizion SO+ AO Vicon SO+ AO	Compensation \$30
12-month trial phase	No session for this group	Telephone follow-up after 2 weeks	0241_CrA_Rencontre2_Journal_VF
Session 3 (2 months)	No session for this group	Cryovizion SO+ AO+ PN Vicon SO+ AO+ PN	Compensation \$40 0241_CrA_QuestionnaireSession345_VF 0241_CrA_Rencontre2_Journal_VF (Verification)
Session 4 (6 months)	No session for this group	Cryovizion SO + AO + PN Vicon SO + AO + PN	Compensation \$50 0241_CrA_Questionnaire_Rencontre345_VF 0241_CrA_Rencontre2_Journal_VF (Verification)
Session 5 (12 months)	No session for this group	Cryovizion SO + AO + PN Vicon SO + AO + PN	Compensation \$80 0241_CrA_QuestionnaireSession345_VF 0241_CrA_Rencontre2_Journal_VF (Verification)

The orthoses are modeled and manufactured by 3D SLS printing for plat/creux participants only, with data from encounter 1 by partner company Cryos. They are then sent to Topmed.

Data processing

Biomechanical data processing.

Cryovizion data processing

Data recording: Questionnaires.

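### The 95% accuracy target for Cryovizion concerns standing, whole-body posture, but its evident comparator, Vicon, is described only in walking and on the lower limbs

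*Protocol*

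**What the plan says.** Under State of knowledge and project relevance, the protocol says the Cryos system is already in use in podiatry practices, "but has never been formally validated in terms of the effect of manufactured orthotics and postural analysis". Research objectives then gives the only numerical performance target in the document: "The cryovizion system should detect changes in participants' posture with 95% accuracy".

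The instruments are described under Measurement, assessment and data collection tools:

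- **Vicon.** This "motion capture system will provide more precise data as participants walk". Its sensors are "strategically positioned at anatomical landmarks on the participants' lower limbs". The paragraph ends: "This validation system is non-invasive and harmless to health". No other instrument is described as a validation system.
- **Force platforms.** "Load distribution between the legs will be analyzed using two AMTI force platforms". No task is given.
- **Cryovizion.** It assesses body symmetry: "subjects are instructed to stand up straight, wearing their underwear. Images are acquired from the front, side and back, from head to toe".

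Scientific justification for using live subjects promises comparison data from a validated system, which it does not name, to confirm the orthosis effects seen with Cryovizion. The Sessions schedule lists Cryovizion and Vicon by footwear only: barefoot (PN), shod without orthoses (SO) and shod with orthoses (AO). It gives no task for either system.

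**The concern.** An accuracy figure needs a reference that observes the same thing as the device under test. Here the device records a person standing still, head to toe. The comparator is described as recording the legs of a person who is walking.

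Suppose Cryovizion shows a change in symmetry and Vicon does not. Cryovizion may be wrong, or standing posture may have changed while gait did not. With walking data alone these explanations cannot be told apart, so agreement with Vicon is not accuracy for posture. For the trunk, shoulders and head there is no described reference at all.

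Validating Cryovizion is one of the two stated aims, and the 95% is its only quantified criterion. A statistical analysis plan may define accuracy, the variables and the threshold for a change. It cannot supply a task or body region that was not recorded.

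**Working it through.** **No figure to reproduce.** The 95% is a target with no calculation behind it. The check compares the descriptions and then counts the pairing.

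**Step 1: descriptions side by side.**

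| | Cryovizion | Vicon | Force platforms |
|---|---|---|---|
| Task | standing upright | walking | not stated |
| Body region | head to toe | lower limbs | load under each leg |
| Role | device to be validated | described as a validation system | load distribution |

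Task and region differ between the first two columns. If recorded in standing, the platforms could give a partial left-right reference for load, but load is not alignment.

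**Step 2: is Vicon the comparator?** No sentence ties it to the 95%. Three places point to it: its description as a validation system, the promise of comparison data from a validated system, and its place beside Cryovizion in the schedule. Together they make it the evident comparator.

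**Step 3: pairing by session and footwear.** Inputs are 20 controls, 30 flat-foot and 30 hollow-foot participants (so 60 flat/hollow) and the Sessions schedule, assuming full completion. The unit is one participant in one session and one footwear condition, not one image.

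Per flat/hollow participant:

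| Session | Cryovizion | Also Vicon |
|---|---|---|
| 1 | 1 (PN) | 0 |
| 2 | 2 (SO, AO) | 2 |
| 3 | 3 (SO, AO, PN) | 3 |
| 4 | 3 | 3 |
| 5 | 3 | 3 |
| Total | 12 | 11 |

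Per control: 2 Cryovizion conditions (PN, SO), both with Vicon.

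- Cryovizion conditions: 60 × 12 + 20 × 2 = 720 + 40 = 760.
- With Vicon in the same session and footwear: 60 × 11 + 20 × 2 = 660 + 40 = 700.
- Without: 760 − 700 = 60, all of them session 1 barefoot in flat/hollow participants.

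The schedule is therefore well paired: 700/760 = 92%. The defect lies in what is recorded within each pair.

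**Step 4: what a standing capture would change.** Added to the 700 paired conditions, it would give lower-limb quantities in the same stance from both systems. It would not close the upper-body gap, because the sensors are described on the lower limbs only.

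**The case against.** The strongest reply is that the task gap rests on silence. The schedule names no task for either system, so a standing Vicon capture may well be made without being described. The walking description is essentially one clause in a document translated from French. The section heading is weak support, because in the text as read the Cryovizion paragraph, which describes standing, falls under the same walking-pattern heading. This stands in part: the documents do not show that standing captures are not made. A reader might infer that Vicon never records standing, and that goes too far. Walking is nevertheless the only task the protocol gives for Vicon, and the body-region gap does not depend on the point.

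A second reply is that the stated purpose of the comparison is to corroborate orthosis effects, for which walking data can serve. That is right. It supports keeping the walking comparison, but not reading it as a 95% accuracy figure for posture.

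Two further readings are tempting and not supported:

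- **That the target has no reference at all.** Read together, the document makes Vicon the evident comparator. The definition of accuracy may properly sit in an analysis plan that is not shown.
- **That the barefoot baseline is lost.** The protocol places pre-test biomechanical data at session 2, so session 1 barefoot need not be the baseline. The contrast of SO with AO is paired in all four sessions where it occurs. What remains is minor: session 1 barefoot Cryovizion in flat/hollow participants has no paired Vicon and should stay out of the accuracy comparison.

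**Conclusion.** The point holds for the plan as described. Following the text as written would not yield a 95% accuracy figure for standing, whole-body posture. The task mismatch applies to all 700 paired conditions unless a standing Vicon capture is made that the protocol does not describe. The absence of a reference above the lower limbs holds either way.

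The conclusion rests on Vicon being the intended comparator, which is a strong inference and not an explicit statement, and on the count assuming full completion. The size of any distortion cannot be estimated, because the documents give no figure for how often standing and walking agree on a change.

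A reader might also infer that the orthosis evaluation fails. It does not: comparisons of symmetry within Cryovizion, with versus without orthoses and over time, need no Vicon reference. This is a cheap improvement to the validation aim, not a fault that undermines the trial.

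**What to change.** - In the Vicon paragraph and the Sessions schedule, state a short quiet-standing Vicon capture in the Cryovizion stance for each session and footwear condition where both systems are already listed. If such captures are already made, say so.
- State the task for the force platforms.
- Limit the 95% accuracy claim to named lower-limb quantities that both systems measure in standing, and make no accuracy claim for upper-body alignment.
- Keep session 1 barefoot Cryovizion in flat/hollow participants out of the accuracy comparison.
- Keep the walking data for gait and for corroborating the orthosis effects.
- If collection is complete without standing Vicon data (the scheduled end was June 2023), report the walking comparison as convergent evidence for the orthosis effects, not as 95% accuracy.

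The cost is a sentence or two of text plus 2 captures per control, 2 at session 2 and 3 at each of sessions 3 to 5, with equipment already in the sessions. At an assumed 0.5 to 1 minute each, three captures add 1.5 to 3 minutes to a follow-up session (for example "3rd session (2months) : 1h30 to 2h"). That is between 1.5/120 = 1.25% and 3/90 = 3.3% of its length. The other cost is a narrower claim. If collection is over, only the wording of the claim changes.

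### Pain reduction is a stated purpose of the questionnaires and logbook, but entrants must be pain-free and no pain record is scheduled before the orthoses are delivered

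*Protocol*

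**What the plan says.** Under the measurement, assessment and data collection tools, the Protocol gives the subjective questionnaires and the logbook two purposes: to check comfort in wear, and "to target the extent to which and how pain is reduced".

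The common inclusion criteria, which bind the flat-foot and hollow-foot groups as well as the controls, require participants to have no pain. No site, intensity or duration qualifies this.

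The type of test is described as "Repeated measurements on a single group with pre-tests and follow-up at 2, 6 and 12 months". For the orthosis groups, the participants section describes the pre-test this way: "The second session will be used to try on and adjust the orthoses, and to take pre-test biomechanical data".

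The sessions schedule lists the questionnaire ("0241_CrA_QuestionnaireSession345_VF") at Sessions 3 and 5, and under a slightly different file name at Session 4. The logbook ("0241_CrA_Rencontre2_Journal_VF") first appears in the row for the 12-month trial phase, which follows delivery at Session 2. Neither Session 1 nor Session 2 lists a questionnaire or a pain record.

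On admission, the protocol sequence says "Validation by e-mail or telephone", and then "Appointment: 2 weeks (or more if necessary) between delivery of consent form and first session".

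**The concern.** To say how far pain has fallen, one needs a starting level above zero and a record of it. The eligibility rule removes the first and the schedule does not provide the second. Each gap is enough by itself to defeat the stated purpose.

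The risk lies in interpretation. A participant who enters without pain and reports little or none at 2, 6 and 12 months has shown no relief. Taken against the stated purpose, though, those answers could be reported as a benefit of the orthosis. What this sample can inform is the opposite question, whether pain appears while the orthosis is worn. Even there the reference is only the screened absence of pain. Eligibility is checked remotely, at least 2 weeks before Session 1, and no listed item at Session 1 or Session 2 confirms it.

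**Working it through.** The protocol states no figure for pain, so there is none to reproduce. The check compares the stated purpose with the eligibility rule and the schedule.

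**Inputs from the Protocol.** The orthosis groups have 30 flat-foot and 30 hollow-foot participants, 60 in all (participants section). The questionnaire is listed at three sessions, and the logbook from the trial phase onward (sessions schedule). Entrants must be pain-free (common inclusion criteria).

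**Step 1: records by timing, orthosis groups.**

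| Point | Pain-related record listed |
|---|---|
| Session 1 | none |
| Session 2 (delivery) | none |
| Trial phase | logbook |
| Sessions 3, 4, 5 | questionnaire, logbook check |

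Planned questionnaires after delivery: 60 x 3 = 180. Listed pain records before delivery: 0.

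**Step 2: criterion enforced.** Pain before the orthosis is zero for every participant. On any scale that cannot go below zero, change from entry is zero or an increase. Participants able to show a reduction: 0 of 60.

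**Step 3: criterion applied loosely.** The protocol gives no rate of pain at entry, so a range is assumed:

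- 5%: 60 x 0.05 = 3 participants
- 10%: 60 x 0.10 = 6 participants
- 20%: 60 x 0.20 = 12 participants

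If each of them had 2 points on a 0-10 scale (also assumed) and lost all of it, the mean reduction over 60 would be 3 x 2 / 60 = 0.1, 6 x 2 / 60 = 0.2 or 12 x 2 / 60 = 0.4 points. The schedule provides no earlier score by which to identify these participants.

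**Step 4: other comparators.** Controls have no session after Session 1, so there is no orthosis-free follow-up to stand in for a baseline.

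**Step 5: what a restated measure could give.** Assume no dropout and no participant with new pain. The one-sided exact 95% upper limit for the proportion affected is 1 - 0.05^(1/n):

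- n = 60: 1 - 0.05^(1/60) = 4.9%
- n = 30 (one foot type): 1 - 0.05^(1/30) = 9.5%

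This step describes the replacement measure. The finding does not depend on it.

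**The case against.** The strongest reply is that the protocol names no reference level for the reduction. The forms might track pain that starts after fitting and later subsides, or compare pain with and without the orthosis, as the biomechanical sessions do. Both are possible, and either could be recorded after delivery. But neither is a reduction from a pre-orthosis level, which is the plain reading of the clause and the only claim made here.

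Second, the contents of several forms are not shown. The admission form may ask about pain, the joint assessment at Session 1 may touch on it, and the logbook's file name ties it to the second meeting. This point stands in part: what is established is that the schedule names no pain item before delivery, not that no form contains one. For anyone properly admitted, however, a screening answer could only confirm the absence of pain.

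Third, the text is a translation, and the pain criterion may have been meant more narrowly. The document does not say so, and a narrower meaning would make the unscheduled baseline matter more.

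Fourth, pain is not among the research objectives, no pain hypothesis is stated, and the protocol says results will not be published. That limits the seriousness but does not remove the conflict: pain reduction is one of only two purposes given for these instruments.

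Finally, the assumed entry rates have no anchor in the protocol. That is correct; they illustrate scale and the conclusion does not need them.

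**Conclusion.** The concern holds. The stated pain purpose, the pain-free entry criterion and the schedule cannot be satisfied together, and nothing else in the protocol reconciles them. With the criterion enforced, 0 of 60 participants can show a reduction. With it applied loosely, perhaps 3 to 12 of 60 could (assumed 5% to 20%), but no scheduled pre-orthosis score would identify them or measure their change.

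A later analysis plan cannot repair this, because it cannot supply a baseline that was not collected or give pain-free entrants pain to lose. The conclusion rests on reading the clause as reduction from the level before the orthosis, and on the forms as scheduled, since their contents are not shown.

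The consequence is confined to a secondary, subjective measure. The comfort purpose and the imaging and postural-symmetry objectives stand. It should be fixed, but it does not threaten the main aims.

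**What to change.** 1. In the questionnaire paragraph, replace "to target the extent to which and how pain is reduced" with wording such as *to record new or worsened pain during orthosis wear*. Leave the comfort purpose as it is, and draw no conclusion about pain relief.
2. Add one short pain item at Session 2, before the orthoses are tried on, and repeat the same item at Sessions 3 to 5. It confirms the pain-free start and gives later answers a measured reference. *Worsened* applies only to anyone whose Session 2 answer is above zero.

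The cost is one reworded clause and 60 short items at an existing 2-hour visit. At an assumed 2 to 5 minutes each, that is 60 x 2 = 120 minutes to 60 x 5 = 300 minutes, or 2 to 5 hours in total. No visit or eligibility rule changes.

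The downside is that the sponsor gives up any claim of pain relief from this sample. One limit remains: controls are not followed, so new pain during wear would have no concurrent comparator and should be reported descriptively.
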